Study Protocol and Statistical Analysis Plan

**Official Title: Combined Muscle Energy
Technique and Myofascial Chain
Stabilization Reduces Menstrual Pain and
Improves Pelvic Alignment in Women With
Primary Dysmenorrhea: A Prospective Study**

NCT Number: [Pending]

Date: December 10, 2024

Combined Muscle Energy Technique and Myofascial Chain Stabilization Reduces Menstrual Pain and Improves Pelvic Alignment in Women With Primary Dysmenorrhea: A Prospective Study

NCT Number: [Pending]

Document Date: December 10, 2024

1. Background and Rationale

Primary dysmenorrhea (PD), defined as menstrual pain without identifiable organic pathology, affects up to 90% of women of reproductive age. Conventional treatments, including NSAIDs and hormonal contraceptives, often offer only temporary relief. Emerging evidence indicates that pelvic girdle dysfunction and spino-pelvic misalignment are potential contributors to pain in PD. Abnormalities in pelvic tilt (PT), sacral slope (SS), and pelvic incidence (PI) may increase myofascial tension and impair neuromuscular coordination, thereby exacerbating menstrual discomfort. These musculoskeletal impairments may also contribute to altered uterine positioning and reduced pelvic circulation, mechanisms that have been linked to elevated prostaglandin activity and increased menstrual pain.

Muscle Energy Technique (MET) and myofascial chain-based pelvic stabilization training have been proposed as non-pharmacologic interventions targeting structural dysfunction and neuromotor control. This protocol outlines a prospective clinical trial comparing the efficacy of these techniques against conventional physiotherapy.

2. Objectives

Primary Objective:

To evaluate the effects of combined MET and myofascial chain stabilization training on pelvic alignment and menstrual pain in women with moderate-to-severe PD.

Secondary Objectives:

To assess changes in static balance (single-leg stance time, eyes closed) and pelvic symmetry (radiographic composite score) as functional correlates of biomechanical improvement.

3. Study Design

This study is a prospective, non-randomized controlled clinical trial conducted over four weeks of active intervention, with an additional 12-week follow-up via telephone. A 12-week post-intervention telephone follow-up will assess long-term effects. Participants

were assigned to either the Combined MET and MFC-Based Pelvic Stabilization group or the Conventional Physiotherapy group.

4. Participants

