4.1 Inclusion Criteria

- Female, aged 18–45 years
- Regular menstrual cycles
- Clinical diagnosis of primary dysmenorrhea
- VAS score ≥ 4 during menstruation for at least six consecutive months
- Radiographic evidence of abnormal PT, SS, or pelvic asymmetry

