5.1 Combined MET and MFC-Based Pelvic Stabilization Group (n = 15)

Participants received:

- Muscle Energy Technique (MET) for iliac dysfunction and sacral torsion
- Pelvic stabilization training based on myofascial chain principles, including curl-ups, planks, and anti-rotation exercises
- Frequency: 3 sessions per week, 50 minutes per session, for 4 weeks

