5.2 Conventional Physiotherapy Group (n = 15)

Participants received:

- Medium- and low-frequency electrotherapy
- Deep friction massage in the sacroiliac and iliac crest regions

- Frequency: 3 sessions per week, 50 minutes per session, for 4 weeks

All treatments were administered by licensed physical therapists.

6. Outcome Measures

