6.1 Primary Outcome

- Change in average menstrual pain intensity measured by Visual Analog Scale (VAS, 0–10), from baseline to Week 4 and at 12-week follow-up.

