6.2 Secondary Outcomes

- 1) Change in pelvic tilt (PT) measured by lateral radiograph (degrees)
- 2) Change in sacral slope (SS) measured by lateral radiograph (degrees)
- 3) Change in pelvic incidence (PI) measured by lateral radiograph (degrees)
- 4) Change in pelvic symmetry measured by X-ray composite score
- 5) Change in static balance measured by single-leg stance time (eyes closed, seconds)

7. Statistical Analysis Plan

All statistical analyses were conducted using SPSS version 27.0. The significance level was set at $p < 0.05$.

- Normality Testing: Shapiro–Wilk test
- Baseline Homogeneity: Independent sample t-tests for continuous variables
- Within-Group Comparisons: Paired sample t-tests for pre-post changes
- Between-Group Comparisons: ANCOVA with baseline scores as covariates
- Effect Sizes: Hedges' g for small-sample corrections

8. Ethics and Trial Registration

This study was approved by the Institutional Review Board of Shenzhen University General Hospital (Approval No.: 2025-Ethics-1-YLT). Written informed consent was obtained from all participants prior to enrollment. Clinical trial registration is in progress at ClinicalTrials.gov (NCT Number: [Pending]).

9. Appendices

Figure 1. Study design flowchart

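### Does taking the 12-week primary VAS score over the telephone undermine the long-term result?

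*Combined protocol and SAP*

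**What the plan says.** The primary outcome in Section 6.1 is "Change in average menstrual pain intensity measured by Visual Analog Scale (VAS, 0–10), from baseline to Week 4 and at 12-week follow-up". Section 3 describes the later contact twice, first as four weeks of treatment "with an additional 12-week follow-up via telephone" and then in the sentence "A 12-week post-intervention telephone follow-up will assess long-term effects".

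The VAS is mentioned in only one other place, the entry criterion in Section 4.1: "VAS score ≥ 4 during menstruation for at least six consecutive months". Neither mention says whether the score is marked on a line, written as a number, spoken or recalled. Section 7 plans paired t-tests for change within each group and ANCOVA adjusted for baseline between groups. It does not say which of these is applied at 12 weeks. Section 5 gives 15 participants per arm. Figure 1, the design flowchart, is not available in the text reviewed.

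**The concern.** A visual scale is commonly a line that the respondent sees and marks, and a telephone call cannot carry that mark. If the baseline and Week 4 scores were marked and the 12-week score spoken, the change from baseline to 12 weeks within an arm would combine true change with a change of instrument, and the data could not separate the two.

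The 12-week assessment also rests on this one score. Four of the five secondary outcomes in Section 6.2 need radiographs and the fifth is a timed test, "Change in static balance measured by single-leg stance time (eyes closed, seconds", so pain is the only listed outcome that a call can supply. At stake would be a statement that relief lasted, or faded, within an arm.

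**Working it through.** **Step 1. What the text establishes.**

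| Time point | Contact | Mode of VAS |
|---|---|---|
| Screening (Section 4.1) | not stated | not stated |
| Baseline (Section 6.1) | not stated | not stated |
| Week 4 (Section 6.1) | not stated | not stated |
| 12 weeks (Sections 3 and 6.1) | telephone | not stated |

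The telephone is the only fixed element. No line, millimetre reading, paper form or diary is mentioned, and the scale is given as 0–10. A spoken 0–10 rating at every time point is consistent with all four rows. So is a mixture of modes. The text does not decide between them.

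**Step 2. The within-arm comparison, if the mode did change.** The documents give neither a shift nor an SD, so these are assumptions: shift d = 0.25 or 0.5 points, SD of change s = 1.5, 2.0 or 2.5, no true change. From Section 5, n = 15. For a two-sided paired t-test at 0.05 with 14 degrees of freedom, the critical value is 2.145, the noncentrality is d√n/s, and the 95% half-width is 2.145 × s/√15.

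| s | Half-width | Rejection, d = 0.25 | Rejection, d = 0.5 |
|---|---|---|---|
| 1.5 | 0.83 | 9.2% | 22.5% |
| 2.0 | 1.11 | 7.4% | 14.7% |
| 2.5 | 1.38 | 6.5% | 11.2% |

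For example, d = 0.5 and s = 1.5 give a noncentrality of 0.5 × 3.873/1.5 = 1.29 and 22.5% rejection, the extreme corner. The assumed shifts are 18% (0.25/1.38) to 60% (0.5/0.83) of the half-width.

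The 5% reference is itself generous. Entry requires a score of at least 4, so regression to the mean and natural course would move an uncontrolled before-and-after test off 5% with no change of mode. The sign of a mode shift is also unknown: it could add to that drift or offset it.

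**Step 3. The between-group comparison.** Write the 12-week score as a + τ·group + β·baseline + error. A shift d common to both arms replaces a by a + d and leaves τ untouched. Simulation agrees. With 15 per arm, an assumed baseline-to-12-week correlation of 0.5, no true effect and 100,000 runs, a common shift of 0.5 gave a mean estimate of 0.00 and rejection of 4.8%, 4.9% and 4.9% for SD of change 1.5, 2.0 and 2.5.

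Only a shift that differs between arms biases τ. A difference of 0.25 gave a mean estimate of 0.25 and rejection of 7.9%, 6.6% and 6.1%. Nothing in the documents suggests that the arms would be telephoned or scored differently.

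**Step 4. Which analysis answers the trial's question.** Section 1 sets out a comparison of the combined techniques with conventional physiotherapy. That is the ANCOVA, the analysis a common shift leaves alone. The paired tests in Section 7 read most naturally as before versus after the four weeks of treatment. Their use at 12 weeks is possible but not stated.

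**The case for a change.** The strongest case for acting is that a primary-outcome time point has no stated means of collection, that the whole long-term assessment depends on it, and that one sentence would settle the matter. Section 7 does not rule out a paired test at 12 weeks. Treatment is described in the past tense ("Participants received") and the call in the future, so the 12-week score might still be matched to the earlier ones, for instance with a form completed at home and the call as a reminder.

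The factual part stands: the mode is unstated at every time point, and a reader cannot confirm that it was constant. The rest is weaker. The tenses are a poor guide to what is still open, because Section 7 also describes the analyses as already done. The home form presumes that earlier scores were marked on a form; if they were spoken, it would create the very change of mode it is meant to prevent. Holding the mode constant is ordinary practice and needs no redesign. The period over which pain is averaged, and the cycle to which the 12-week score refers, are also unstated, but that is a separate matter from the telephone.

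**Conclusion.** The concern does not hold as a fault in the design. It identifies a missing detail of administration that the trial team can fill sensibly by asking for the 0–10 score in the same way throughout and saying so in the report. Using the telephone for a 12-week contact in a 30-participant study (2 × 15) is a fair trade-off for an outcome that participants report themselves.

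The possible damage is confined to a within-arm statement out to 12 weeks, which regression to the mean and natural course already make weak evidence. Under the assumed shifts and SDs the false-positive rate there would be 6.5% to 22.5%, conditional on a mode change and a paired test that the documents do not show. The between-group estimate has bias 0.00 under a common shift, and the Week 4 result is touched only if its mode differed from baseline, which is also not shown.

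This judgement rests on the available text without Figure 1, and on both arms being contacted in the same way at 12 weeks. Evidence that the arms were scored by different modes would change it.

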4.1 Inclusion Criteria

- Female, aged 18–45 years
- Regular menstrual cycles
- Clinical diagnosis of primary dysmenorrhea
- VAS score ≥ 4 during menstruation for at least six consecutive months
- Radiographic evidence of abnormal PT, SS, or pelvic asymmetry

4.2 Exclusion Criteria

- Secondary dysmenorrhea or gynecologic pathology
- Pregnancy or ongoing hormone therapy
- Congenital or structural musculoskeletal disorders
- Concurrent participation in other physiotherapy interventions

All participants provided written informed consent prior to enrollment.

5. Interventions

5.1 Combined MET and MFC-Based Pelvic Stabilization Group (n = 15)

Participants received:

- Muscle Energy Technique (MET) for iliac dysfunction and sacral torsion
- Pelvic stabilization training based on myofascial chain principles, including curl-ups, planks, and anti-rotation exercises
- Frequency: 3 sessions per week, 50 minutes per session, for 4 weeks

5.2 Conventional Physiotherapy Group (n = 15)

Participants received:

- Medium- and low-frequency electrotherapy
- Deep friction massage in the sacroiliac and iliac crest regions

- Frequency: 3 sessions per week, 50 minutes per session, for 4 weeks

All treatments were administered by licensed physical therapists.

6. Outcome Measures

6.1 Primary Outcome

- Change in average menstrual pain intensity measured by Visual Analog Scale (VAS, 0–10), from baseline to Week 4 and at 12-week follow-up.

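### Menstrual pain VAS is primary at two time points with no success rule; if either suffices, family-wise error is about 7–10%. Sections 2 and 6.2 also disagree on pelvic alignment

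*Combined protocol and SAP*

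**What the plan says.** - **Section 6.1** names one primary outcome, change in average menstrual pain on a 0–10 VAS, at two times: "from baseline to Week 4 and at 12-week follow-up".
- **Section 7** gives a single threshold: "The significance level was set at" p < 0.05. Between-group comparisons are by ANCOVA with the baseline score as covariate, and pre-post changes within each arm are by paired t-test. The ANCOVA is not tied to a time point, and neither test is named as decisive.
- **Section 1** describes the trial as "comparing the efficacy of these techniques against conventional physiotherapy", so the natural efficacy test is the between-arm one.
- **Section 3** gives the later assessment a purpose but no rank: "A 12-week post-intervention telephone follow-up will assess long-term effects".
- **Section 2** states the primary objective as "To evaluate the effects of combined MET and myofascial chain stabilization training on pelvic alignment and menstrual pain in women with moderate-to-severe PD". Section 6.2 lists pelvic tilt (PT), sacral slope (SS) and pelvic incidence (PI) only as secondary outcomes. Pelvic symmetry is secondary in both sections.

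**The concern.** With two primary results and one unadjusted threshold, the plan's silence allows a primary claim to rest on whichever time point falls below 0.05. The chance of a false primary claim is then above 5% even if the two arms are fully comparable. A reader of the final report could not tell whether a result at one time only, at Week 4 or at the 12-week follow-up, counts as success.

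The alignment mismatch raises the same question for a different claim. The official title announces both less pain and better alignment. Section 2 supports treating alignment as confirmatory, and section 6 does not.

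**Working it through.** The plan states no family-wise error, sample-size derivation, SD or correlation, so there is no figure of its own to reproduce beyond the nominal 0.05.

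**Inputs from the document.** Two primary time points (section 6.1); level 0.05 (section 7); baseline-adjusted ANCOVA (section 7); 15 per arm (sections 5.1 and 5.2). Residual degrees of freedom are 30 − 3 = 27 with no dropout.

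**Inputs assumed.** Two-sided tests, no true effect at either time, complete data, normally distributed VAS, no confounding, and the correlations shown below.

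**Step 1: closed form.** Let ρ be the correlation between the two test statistics.

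- Either suffices: P(either) = 1 − P(|Z₁| < 1.96 and |Z₂| < 1.96). At ρ = 0 this is 1 − 0.95² = 9.75%. It cannot exceed 0.05 + 0.05 = 10%.
- Both required: P(both) = 0.05 + 0.05 − P(either). At ρ = 0.5 this is 10% − 9.07% = 0.93%.

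| ρ | Either at 0.05 | Both at 0.05 | Either at 0.025 each |
|---|---|---|---|
| 0 | 9.75% | 0.25% | 4.9% |
| 0.3 | 9.5% | 0.5% | 4.8% |
| 0.5 | 9.1% | 0.9% | 4.65% |
| 0.7 | 8.35% | 1.65% | 4.3% |
| 0.9 | 7.0% | 3.0% | 3.6% |

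**Step 2: which ρ is plausible.** After adjustment for baseline, ρ is close to the partial correlation of the two follow-up values, (r₁₂ − r₀₁r₀₂) / √[(1 − r₀₁²)(1 − r₀₂²)], where 0 is baseline, 1 is Week 4 and 2 is the 12-week follow-up. If all three correlations equal r, this reduces to r/(1 + r). For r = 0.5 it is 0.5/1.5 = 0.33. For r₀₁ = r₀₂ = 0.3 and r₁₂ = 0.9 it is (0.9 − 0.09)/0.91 = 0.89.

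**Step 3: simulation of the ANCOVAs** (15 per arm, 27 df, 200,000 trials per setting).

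| VAS correlations r₀₁, r₀₂, r₁₂ | Either suffices |
|---|---|
| 0.3, 0.3, 0.3 | 9.6% |
| 0.5, 0.5, 0.5 | 9.5% |
| 0.7, 0.7, 0.7 | 9.3% |
| 0.9, 0.9, 0.9 | 9.2% |
| 0.5, 0.3, 0.7 | 8.5% |
| 0.3, 0.3, 0.8 | 8.0% |
| 0.3, 0.3, 0.9 | 7.2% |

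In the four equal-correlation settings, Week 4 alone rejects 4.9–5.0% of the time, 0.025 each gives 4.7–4.8%, and requiring both gives 0.4–0.8%. Testing Week 4 first has the same error as Week 4 alone, because no claim is possible without it.

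**Step 4: cost in power.** Assume VAS correlation 0.5 throughout (100,000 trials).

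| Chance of any primary claim | Effect 1.0 SD at both times | 1.0 SD at Week 4, 0.5 SD at 12 weeks |
|---|---|---|
| Week 4 first | 85% | 85% |
| 0.025 each | 91% | 79% |
| Both required | 74% | 30% |
| Either, uncontrolled | 96% | 87% |

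With Week 4 first, a 12-week claim needs both results. Its chance falls from 85% to 74% in the first scenario and from 32% to 30% in the second.

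**Step 5: alignment.** This needs no arithmetic. Section 2 names alignment and pain together as primary, section 6.1 has VAS alone, and section 6.2 has PT, SS and PI as secondary. No other section settles which governs.

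**The case against.** The strongest reply is that section 6.1 joins the two times with the word *and*. Read literally, both are required and the error is at most 5%. The wording may also be no more than a measurement schedule. This stands to the extent that what is shown is an ambiguity, not an uncontrolled test that the sponsor has adopted. It does not close the point, because a conjunction in an outcome definition is not a decision rule and section 7 supplies none.

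Four stronger readings are tempting, and the document does not support them:

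- *The plan's error rate is a single figure such as 9%.* That fits a test correlation of about 0.5. The correlation is not given, and values of 7% or nearly 10% are equally compatible with the document.
- *Alignment adds further primary tests, so the inflation is larger still.* Section 6 lists VAS as the only primary outcome. The conflict with section 2 is one of wording to be reconciled, not evidence that PT, SS and PI are tested as primary.
- *The past tense in section 7 ("All statistical analyses were conducted using SPSS version 27.0") shows that the outcomes were already known.* Section 3 still speaks of the telephone follow-up in the future. The tenses raise the question of when a rule would be set, and do not answer it.
- *With a rule in place, the 5% is assured.* Section 3 says: "This study is a prospective, non-randomized controlled clinical trial". Confounding would be a problem with one endpoint or two. It neither supports nor sizes the multiplicity point, and no multiplicity rule removes it.

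It is also fair to say that testing Week 4 first is a preference. The long-term purpose given in section 3 is consistent with that order but does not require it.

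**Conclusion.** The point holds as an unresolved decision rule for the primary outcome, and it should be fixed. If either time point suffices, family-wise error is about 7–10% instead of 5%: 7.0–9.75% in closed form for test correlations from 0.9 to 0, and 7.2–9.6% in the simulated ANCOVAs. It would fall to 5% only if the two tests were perfectly correlated. All of these figures rest on the assumptions listed with the inputs above, including no loss at the telephone follow-up. If both are required there is no inflation, but the plan does not state this.

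The disagreement between sections 2 and 6.2 on PT, SS and PI is certain from the text and depends on no assumption.

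**What to change.** State one success rule in sections 6 and 7. Possible text: *The decisive test is the between-arm ANCOVA of VAS at Week 4, adjusted for baseline VAS, at two-sided 0.05. VAS at the 12-week follow-up is tested by the same ANCOVA at 0.05 only if Week 4 is significant.* Requiring both, or 0.025 each, is also valid; the sponsor should choose one and write it down.

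In the same edit:

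- State that the within-arm paired tests are descriptive and carry no efficacy claim.
- Make section 2 agree with section 6, most simply by moving alignment to the secondary objectives. If alignment is to stay primary, name the parameter and bring it under the same error rule.
- Give a dated statement of whether outcome data had been seen when the rule was set. If they had, disclose the rule as post hoc.
- Add one sentence saying that the rule controls multiplicity only, not confounding from non-random allocation.

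The cost is a few sentences and no new data. The downside of testing Week 4 first is that no 12-week claim is possible if Week 4 fails, with the loss of power shown in Step 4. Moving alignment to the secondary objectives gives up any confirmatory claim on it.

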6.2 Secondary Outcomes

- 1) Change in pelvic tilt (PT) measured by lateral radiograph (degrees)
- 2) Change in sacral slope (SS) measured by lateral radiograph (degrees)
- 3) Change in pelvic incidence (PI) measured by lateral radiograph (degrees)
- 4) Change in pelvic symmetry measured by X-ray composite score
- 5) Change in static balance measured by single-leg stance time (eyes closed, seconds)

7. Statistical Analysis Plan

All statistical analyses were conducted using SPSS version 27.0. The significance level was set at $p < 0.05$.

- Normality Testing: Shapiro–Wilk test
- Baseline Homogeneity: Independent sample t-tests for continuous variables
- Within-Group Comparisons: Paired sample t-tests for pre-post changes
- Between-Group Comparisons: ANCOVA with baseline scores as covariates
- Effect Sizes: Hedges' g for small-sample corrections

8. Ethics and Trial Registration

This study was approved by the Institutional Review Board of Shenzhen University General Hospital (Approval No.: 2025-Ethics-1-YLT). Written informed consent was obtained from all participants prior to enrollment. Clinical trial registration is in progress at ClinicalTrials.gov (NCT Number: [Pending]).

9. Appendices

Figure 1. Study design flowchart

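### Pelvic alignment is in the title and the primary objective, but no alignment measure is primary, and three or four X-ray measures are each tested at 0.05 with no rule for what counts as improvement

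*Combined protocol and SAP*

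**What the plan says.** - **Title.** It asserts an effect on both domains: "Reduces Menstrual Pain and Improves Pelvic Alignment in Women With Primary Dysmenorrhea".
- **Section 2, primary objective.** "To evaluate the effects of combined MET and myofascial chain stabilization training on pelvic alignment and menstrual pain". Pain and alignment are named jointly. Pelvic symmetry (the radiographic composite) appears separately, under the secondary objectives, next to static balance.
- **Section 6.1.** The primary outcome is pain only: "Change in average menstrual pain intensity measured by Visual Analog Scale (VAS, 0–10), from baseline to Week 4 and at 12-week follow-up".
- **Section 6.2.** The radiographic measures are all secondary and unranked. The list opens with "Change in pelvic tilt (PT) measured by lateral radiograph (degrees", continues with SS and PI, and has as its fourth item "Change in pelvic symmetry measured by X-ray composite score".
- **Section 7.** One level, p < 0.05, covers everything ("The significance level was set at"). Arms are compared by "Between-Group Comparisons: ANCOVA with baseline scores as covariates", and paired t-tests are planned within each arm. The section gives no adjustment, no order of testing, no sidedness, and no definition of improved alignment.

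**The concern.** Secondary outcomes are often left unadjusted because no firm claim rests on them. That reasoning does not fit here: alignment is half of the primary objective and half of what the title asserts. The plan has no alignment endpoint to decide that half. It offers several measures, each with its own test at 0.05, and leaves open which result would support the claim.

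The direction of benefit is also open. Section 4.1 requires abnormal PT or SS, or asymmetry, without saying whether abnormal means high or low, and Section 6.2 lists changes without a favourable sign. At stake is whether a statement that treatment improves alignment has the 5% error rate that a reader would assume from the stated level.

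**Working it through.** The documents state no familywise error rate, so there is no figure to reproduce.

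**Inputs**

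- Level per test: 0.05 (Section 7).
- Measures k: 3 if alignment means PT, SS and PI; 4 if the symmetry score also counts (Section 6.2 lists four; Section 2 puts symmetry under the secondary objectives).
- Sample size: 15 per arm (Sections 5.1 and 5.2).
- Assumed: two-sided tests, and one between-arm test per measure.

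**1. Either direction, independent measures:** 1 − 0.95^k

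- k = 3: 1 − 0.8574 = 14.3% (bound under any dependence 3 × 0.05 = 15%)
- k = 4: 1 − 0.8145 = 18.5% (bound 4 × 0.05 = 20%)

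**2. Favouring the combined arm only:** a two-sided 0.05 test puts 0.025 in that tail, so 1 − 0.975^k

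- k = 3: 1 − 0.9269 = 7.3% (bound 7.5%)
- k = 4: 1 − 0.9037 = 9.6% (bound 10%)

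**3. Correlated measures.** The documents give no correlations, so these are assumed. The figures come from 100,000 simulated null trials per setting, 15 per arm, four measures, with two-sample t-tests standing in for ANCOVA.

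| Assumed common correlation | Either direction | Favouring combined arm |
|---|---|---|
| 0.3 | 17.5% | 8.8% |
| 0.5 | 15.6% | 7.8% |
| 0.8 | 11.5% | 5.7% |

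**4. Effect of adjustment.** Holm's first threshold is 0.05/k.

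- k = 4: 0.0125, and 1 − 0.9875^4 = 4.9% if independent
- k = 3: 0.0167, and 1 − (1 − 0.05/3)^3 = 4.9% if independent
- The familywise rate is at most 5% under any dependence.

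**5. Power cost for a single measure.** Two-sided two-sample t-test, 15 per arm, 28 degrees of freedom. The assumed standardised difference d gives noncentrality d × √(15/2), which is 2.74 for d = 1.0.

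| Assumed d | At 0.05 | At 0.0167 (k = 3) | At 0.0125 (k = 4) |
|---|---|---|---|
| 1.0 | 75% | 58% | 54% |
| 0.8 | 56% | 38% | 33% |

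**The case against.** **These are labelled secondary outcomes.** Section 6 makes pain the sole primary outcome, and leaving secondary tests unadjusted is common. As a description of Section 6 that is correct, but it does not answer the title and Section 2, which treat alignment as a main finding. The mismatch between objective and outcome is the firmest part of the point.

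**A reader might infer a 19% chance of a spurious improvement.** The documents do not support that as it stands. The 18.5% counts significant differences in either direction, including those favouring conventional physiotherapy. With two-sided tests the favourable figure is 9.6% for four measures. The higher figure would apply to improvement only if tests were one-sided at 0.05, or if a shift in either direction could be described as improvement; the plan settles neither. Nor is 18.5% a ceiling: it is the independence value, and the strict bound is 20%.

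**Four measures may be one too many.** Section 2 separates symmetry from the alignment objective, so three is a fair reading. The title does not exclude symmetry, so the count remains open.

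**A reader might also pool every planned test, within and between arms, into one much larger error rate.** That is not sound. The within-arm and between-arm tests use the same data and are not independent. Both arms receive active treatment, so a within-arm change may be real and is not a false positive for a difference between treatments.

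**Adjustment costs power in a trial of 30.** That stands, and it is a reason to consider naming one alignment measure.

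**Conclusion.** The point holds. Alignment is a headline claim with no primary endpoint, no multiplicity control and no decision rule. For three to four independent measures, the chance of at least one false-positive between-arm difference is about 14–19% in either direction, or 7–10% favouring the combined arm.

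These figures assume no true effect on any measure, one between-arm test per measure and, for the 7–10%, two-sided tests with the favourable direction fixed in advance. Positive correlation reduces them: for four measures at an assumed correlation of 0.5, about 16% in either direction and 8% favourable. The figures do not count the paired tests, which are planned at the same level and which nothing in Section 7 bars from being used to support the claim. The inflation is moderate, and a wording change removes it.

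**What to change.** Add to Section 7:

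> The measures that make up pelvic alignment (PT, SS, PI, and symmetry if it is meant to count) and the direction of benefit for each are named before analysis. They are compared between arms by ANCOVA as one family with Holm adjustment. Improved alignment is claimed only for a named measure with a Holm-adjusted p below 0.05 in the stated direction. Within-arm changes are reported as estimates with 95% confidence intervals and carry no claim of treatment effect.

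State sidedness in the same section. Naming a single alignment measure to carry the claim is an acceptable alternative: it removes the multiplicity within alignment and keeps the 0.05 threshold for that measure. Testing VAS first as a gate is optional, and would require one VAS time point to be named, because Section 6.1 gives both Week 4 and the 12-week follow-up.

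**Cost.** No extra participants or data are needed. Under Holm the smallest p-value must be below 0.0125 (four measures) or 0.0167 (three), with the power loss shown in the working.

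**Timing.** Section 7 is written in the past tense. If outcomes have already been examined, label the rule post hoc and report the adjusted p-values on that footing.
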